5.8.4 Return or Destruction of Study Drug

5.9.4.1 – CDX-3379

At the completion of the study, there will be a final reconciliation of drug shipped, drug consumed, and drug remaining. This reconciliation will be logged on the drug reconciliation form, signed and dated. Any discrepancies noted will be investigated, resolved, and documented prior to return or destruction of unused study drug. Drug destroyed on site will be documented in the study files.

CDX-3379 will be supplied by Celldex as open-label stock. The investigational product is to be used only for this protocol and not for any other purpose, and must be kept in an appropriate, secure area (e.g., locked refrigerator/cabinet) and stored in accordance with the conditions specified in this protocol/on the labels.

The investigator will assume responsibility for administration and dispensation of study medication. An accurate record of all study drugs received, dispensed, returned, and destroyed must be maintained. Drug supplies will be inventoried and accounted for throughout the study, and accountability records must be available for inspection at any time and provided to Celldex upon the completion of the study.

Upon receipt of any investigational product, an inventory must be conducted to confirm the quantity and condition of material received, and verification of receipt must be completed and returned in accordance with instructions provided by Celldex.

Resupply of study medication may be requested in accordance with instructions provided by Celldex.

Used, partly used, and/or remaining unused investigational product will be either returned to Celldex or destroyed according to the site's Standard Operating Procedures (SOPs), as directed by Celldex, and a record of this disposition will be maintained.

5.9.4.2 -Trametinib

The investigator or designee must maintain an accurate record of the shipment and dispensing of study treatment in a drug accountability log. Drug accountability will be noted by the CRA during site visits and at

CONFIDENTIAL

the completion of the study. Subjects will be asked to return all unused study treatment and packaging on a regular basis, at the end of the study or at the time of study treatment discontinuation.

At study close-out, and, as appropriate during the course of the study, the investigator will return all used and unused study treatment, packaging, drug labels, and a copy of the completed drug accountability log to the Novartis monitor or to the Novartis address provided in the investigator folder at each site.

Any waste material should be disposed of in accordance with local regulations and according to institutional guidelines. If local regulations disallow storage of empty or pierced vials at the site, the site is able to destroy the vials as per local requirements and procedures. Documentation regarding the local regulations and the destruction of the empty vials will be provided to the Sponsor to ensure full drug accountability.

5.9 Pharmacokinetic Variables and Assessments

Blood samples will be collected to determine the levels of CDX-3379 and Trametinib. Approximately 5 ml of blood will be collected. The time of blood collection must be documented. A laboratory manual will be provided with instructions for collecting, processing, and shipping the samples.

Pharmacokinetic blood samples will be drawn from study patients at the time points indicated in Section 6.6 during the Phase Ib portion of the study. For cycles 1 and 2, blood will be drawn prior to treatment with CDX-3379, following CDX-3379 administration, and one hour after trametinib. On days where both CDX-3379 and trametinib are administered, trametinib will be taken immediately following CDX-3379 infusion. On cycle 3 day 1, blood will be drawn prior to treatment with CDX-3379 for minimum concentration (C_{min}) determination. Serum concentrations will be determined for CDX-3379 and trametinib. All samples will be stored at the CBRD, until future use, which is detailed in the lab manual. Trametinib PK samples will be analyzed by Covance. This study provides the opportunity to assess PK of CDX-3379 in combination with trametinib. We believe that CDX-3379 and trametinib will be well tolerated and safe.

5.10 Biomarker Samples

Biomarker data will be explored from archived tissue and pre-treatment, on-treatment, and disease progression tumor biopsy samples during Phase Ib and from ten subjects during the Phase II portion of the study (five subjects with *NRAS* mutation and five subjects with BRAF/*NRAS* WT melanoma), to assess potential associations with tumor response. These samples will be collected prior to treatment on cycle 1 day 1, on day 14-16 after initial treatment, and at the time of disease progression. These samples will be used to assess additional clinically relevant biomarkers, including but not limited to expression levels of ERBB3, cMET, ERBB2, and EGFR and will include assessment of respective receptor ligands. Efficacy outcomes considered for pre-specified mechanistic biomarker analysis will include PFS, objective response rate, and OS based on investigator assessments.

5.10.1 Archived Tumor Samples

If available, formalin-fixed paraffin embedded tumor samples (either a tumor block or freshly cut slides) from the patient's most recent tumor sampling will be collected for biomarker analysis. Tumor samples obtained at the time of metastasis are preferred over tumor samples obtained at the time of primary diagnosis; however, in the event that both are available for analysis, we ask that samples from both time points should be submitted. Directions and requirements for processing and shipping the archived tumor samples can be found in the laboratory manual.

5.10.2 Tumor Biopsy

Core biopsies are required for the Phase Ib and Phase II portion of the study, in order to perform correlative studies. Core biopsies will be collected pre-treatment, on-treatment (day 14-16), and at the time

CONFIDENTIAL

of progression during Phase Ib and from ten patients during the Phase II portion of the study (five *NRAS* mutant melanoma and five WT melanoma), to assess potential associations with tumor response.

6 Study Procedures

Screening

The screening phase begins once written informed consent is provided and ends after 28 days or when subject receives the first treatment dose.

Subjects must sign an informed consent form (ICF) prior to any study specific screening evaluations, within 28 days prior to the first dose of study treatment. Following completion of screening procedures and verifying subject eligibility based on assessments, the subject will be enrolled via the Interactive Response Technology (IRT) system.

6.1 Visit 1 – Screening

An initial screening visit will occur to ensure subjects meet the inclusion criteria. This visit will include a physical exam and medical history, baseline EKG, ophthalmologic exam, baseline laboratory tests including a comprehensive metabolic panel and a complete blood count, and a clinical evaluation to ensure the patient has no factors that would render them ineligible for the study. Subjects will be required to give information regarding their medical history and melanoma treatment course.

Subjects will undergo screening procedures, including documentation of a medical history, patient demographics, vital signs, and ECOG performance status. Labs drawn will include CBC, chemistry, and coagulation profile. Archival tumor biopsy samples should be obtained from tissue available from any time prior to signing consent for this trial, focusing on samples since last treatment regimen until signing consent for this trial. Pre-treatment tumor biopsy will be performed prior to treatment administration during the screening period. A Pregnancy test will be performed on all women of childbearing potential. Baseline EKG and ECHO screening will be performed. Subjects will be asked to identify all concomitant medications they are or will be taking during the time of the study. Baseline imaging with a full body PET-CT or CT scans of the chest, abdomen, pelvis and areas of disease, along with brain MRI must be completed within 4 weeks prior to study enrollment.

6.2 Visit 2, 4

Visit 2 will consist of the start date of the study treatment, representing day 1 of week 1 of cycle 1. Visit 4 will represent day 1 of week 1 of cycle 2. As with all clinical visits, vital signs and ECOG performance status will be recorded, an ophthalmologic exam will be performed and CBC and chemistry will be drawn from the subject as well as serum samples for PK during the first two cycles of treatment in the Phase 1b group. All assessments must be resulted prior to administration of CDX-3379. Medication review will be performed as will AE assessment and reporting. CDX-3379 will be administered at visit 2 and will continue once every three weeks thereafter until disease progression, unacceptable toxicity, subject decision to withdrawal, study closure, or another reason as determined by the study investigators. Dosing is 15mg/kg IV. Blood will be drawn prior to CDX-3379 infusion, immediately following CDX-3379 infusion. Following infusion and blood draw, trametinib will be started at 2mg and should be taken on a continuous basis as prescribed unless otherwise instructed by study investigators. Blood will be drawn one hour after trametinib administration.

CONFIDENTIAL

6.3 Visit 3, 5

Visit 3 and 5 will represent day 1 of week 2 of cycles 1 and 2, respectively. This visit will include documentation of vital signs, ECOG performance status, current medications, and AE assessment and reporting. Blood will be drawn for CBC, chemistry, and PK.

6.4 Visit 6

Visit 6 will represent day 1 of week 1 of cycle 3. Blood will be drawn for CBC and chemistry, and an ophthalmologic exam will be performed. Serum samples for PK will be obtained before treatment administration. All assessments must be resulted prior to administration of CDX-3379. For each visit thereafter, subjects will be seen and evaluated on the first day of each cycle when they receive CDX-3379. Disease evaluation should be reported every 12 weeks after the first dose of CDX-3379.

6.5 End of Treatment Visit

The end of treatment visit should be completed within 4 weeks of the last dose of the study drug. Vital signs, ECOG performance status, AE assessment and reporting, and disease evaluation should be performed. Blood will be drawn for CBC, chemistry, and PK. Progression tumor biopsy should be obtained within 4 weeks of last dose of study drug (last dose of study drug is calculated from the last dose of trametinib).

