1.6.2 Overlapping Toxicities

Unless a side effect is specific to only trametinib (cardiac (red LVEF), ocular (RPED, RVO), and/or pneumonitis), both drugs should be held together. With the exception of the trametinib specific side effects, all other side effects can be considered from either medication.

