4.5.2 Data Collection and Follow-up for Withdrawn Subjects

When a subject is discontinued from treatment for any reason, they are to undergo the assessments in the end of treatment visit within 4 weeks of the last dose. All subjects who discontinue treatment as a result of an adverse event must be followed until resolution or stabilization of the adverse event. If a subject withdraws from study treatment, attempts should be made to contact the subject to determine the reason(s) for discontinuation. The subject will continue to be followed for survival information every 3 months after completion of the End of Treatment visit. All subjects, including subjects who discontinue treatment for other reasons than progressive disease per RECIST 1.1, should undergo a scan to assess disease status prior to termination from the study.

If a subject does not return to the clinic for the end of treatment visit or is not reached for overall survival follow-up, at least 3 documented attempts, including one via certified mail, should be made to contact the subject. If the subject does not respond to these requests, the date of death should be captured from public records.

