5.4.2 CDX-3379 Administration

The dose of CDX-3379 is 15 mg/kg, administered intravenously every 3 weeks (on day 1 of each 21-day cycle). Subjects will be treated with CDX-3379 until progressive disease, unacceptable toxicity, or other criteria for discontinuation of study treatment.

Subjects will receive CDX-3379 as an IV infusion over 60 ± 5 minutes. As a routine precaution, the investigative site's medical staff is to closely observe patients for the duration of CDX-3379 infusion and for at least 1 hour after the end of the infusion.

The entire contents of the IV bag should be administered through an IV administration set with a low protein binding 0.2-µm in-line filter. Since the compatibility of CDX-3379 with other IV medications and solutions other than normal saline (0.9% [w/v] Sodium Chloride for Injection) is not known, the CDX-3379 solution shall not be infused through an IV line in which other solutions or medications are being co-administered. The date, start time, interruption, and completion time of CDX-3379 administration must be recorded in the source documents.

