6.6 Survival Follow-up

Survival data will be collected via telephone or clinic visits every 3 months (± 10 days) from the date of last treatment (date of last treatment is calculated from the last dose of trametinib) until death, loss to follow-up, withdrawal of consent, study termination by the Sponsor, or up to 5 years. In addition, any new anti-cancer therapies and procedures should be collected and documented. Should subjects refuse or drop out of survival follow-up, attempts should be made to obtain any death information via public records whenever possible.

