The study period during which adverse events must be reported is normally defined as the period from the initiation of any study procedures to the end of the study treatment follow-up. For this study, the study treatment follow-up is defined as 30 days following the last administration of study treatment.

Preexisting Condition

A preexisting condition is one that is present at the start of the study. A preexisting condition should be recorded as an adverse event if the frequency, intensity, or the character of the condition worsens during the study period.

General Physical Examination Findings

At screening, any clinically significant abnormality should be recorded as a preexisting condition. At the end of the study, any new clinically significant findings/abnormalities that meet the definition of an adverse event must also be recorded and documented as an adverse event.

Post-study Adverse Event

All unresolved adverse events should be followed by the investigator until the events are resolved, the subject is lost to follow-up, or the adverse event is otherwise explained. At the last scheduled visit, the investigator should instruct each subject to report any subsequent event(s) that the subject, or the subject's personal physician, believes might reasonably be related to participation in this study. The investigator should notify the study sponsor of any death or adverse event occurring at any time after a subject has discontinued or terminated study participation that may reasonably be related to this study. The sponsor should also be notified if the investigator should become aware of the development of cancer or of a congenital anomaly in a subsequently conceived offspring of a subject that has participated in this study.

Abnormal Laboratory Values

A clinical laboratory abnormality should be documented as an adverse event if any one of the following conditions is met:

- The laboratory abnormality is not otherwise refuted by a repeat test to confirm the abnormality
- The abnormality suggests a disease and/or organ toxicity
- The abnormality is of a degree that requires active management; e.g. change of dose, discontinuation of the drug, more frequent follow-up assessments, further diagnostic investigation, etc.

Abnormal lab values that are not clinically significant are not considered adverse events.

Hospitalization, Prolonged Hospitalization or Surgery

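### Sections 6.5 and 6.6 date the last dose by trametinib only, so if trametinib stops first and CDX-3379 continues, no End of Treatment visit follows the last infusion

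*Combined protocol and SAP*

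**What the plan says.** Five places set the clocks that run from the end of treatment.

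- Section 6.5, visit: "The end of treatment visit should be completed within 4 weeks of the last dose of the study drug". This sentence does not say which drug is meant.
- Section 6.5, progression biopsy: due within 4 weeks of the last dose of study drug, with the note that the "last dose of study drug is calculated from the last dose of trametinib".
- Section 6.6: survival contacts every 3 months (± 10 days) from the last treatment, where the "date of last treatment is calculated from the last dose of trametinib".
- Section 4.5.2: subjects discontinued from treatment for any reason, "they are to undergo the assessments in the end of treatment visit within 4 weeks of the last dose"; they are then "followed for survival information every 3 months after completion of the End of Treatment visit". No drug is named.
- Section 8.1: for adverse event reporting, "the study treatment follow-up is defined as 30 days following the last administration of study treatment". Again no drug is named, nor is one in schedule footnotes 8, 9 and 12.

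The two drugs can stop at different times. Section 1.6.2 holds both together "Unless a side effect is specific to only trametinib", and lists cardiac, ocular and pneumonitis events as the exceptions. Table 1 in Section 1.6.1.2.1 stops trametinib permanently for several of these. Section 1.6.3 foresees permanent discontinuation of either drug. CDX-3379 has its own criteria in Section 5.4.2: "Subjects will be treated with CDX-3379 until progressive disease, unacceptable toxicity, or other criteria for discontinuation of study treatment".

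**The concern.** A single-drug anchor works while both drugs stop together, or while trametinib is the last to stop. It misfires when trametinib stops first. The End of Treatment visit and the survival clock are then triggered by a date that is not the end of treatment.

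What is at stake is the one scheduled assessment after the final CDX-3379 infusion. By Section 6.5 and the schedule, that visit carries the adverse event assessment, blood count, chemistry, pharmacokinetic and immunogenicity samples, disease evaluation and, where applicable, the progression biopsy. If it has been used up early, nothing scheduled replaces it. The remaining visits do not serve the same purpose. Section 6.4 requires day-1 assessments to be resulted before CDX-3379 is given, so the day-1 visit of the last cycle cannot show what followed that infusion. Section 1.6.1.1.1 warns that infusion reactions may be delayed, and Section 1.1.1 predicts a prolonged half-life of the antibody in humans.

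The anchors also conflict with each other, so two sites could reasonably date the same patient's visit differently.

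**Working it through.** The plan states no figure to reproduce. The check is a reading of the passages side by side, then a calendar count.

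**Which date does each clock use?**

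| Place | Clock | Anchor as written |
|---|---|---|
| 6.5, visit sentence | End of Treatment visit, 4 weeks | last dose of study drug, drug not named |
| 6.5, biopsy sentence | Progression biopsy, 4 weeks | last trametinib dose |
| 6.6 | Survival contacts | last trametinib dose |
| 4.5.2 | End of Treatment visit, 4 weeks | last dose, drug not named |
| 4.5.2 | Survival contacts | completion of the End of Treatment visit |
| 8.1 | Adverse event reporting, 30 days | last administration of study treatment |
| 6.7, footnotes 8, 9, 12 | Visit, biopsy, survival | last dose or last treatment, drug not named |

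The only definition of last dose or last treatment supplied for these clocks is trametinib. Its use for the visit in 6.5 is an inference, but a natural one: the definition stands in the same paragraph and defines the same term.

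**How many infusions fall inside the window?** Inputs: CDX-3379 on day 1 of each 21-day cycle (5.4.2); a visit window of 28 days (6.5). Assumption: CDX-3379 continues without delay. Let d be the number of days from the latest infusion to the last trametinib dose, d = 0 to 20. Further infusions come 21k − d days after that dose, for k = 1, 2, and so on. Count those with 0 < 21k − d ≤ 28.

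- k = 1: 21 − d is at most 21, so this infusion is always inside.
- k = 2: 42 − d ≤ 28 requires d ≥ 14.
- Result: one further infusion for d = 0 to 13 (14 of 21 stop days), two for d = 14 to 20 (7 of 21).

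For the first survival contact, take 3 months as 91 days, so 81 to 101 days with the ± 10. The largest k with 21k − d within the limit is:

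- at 81 days: 3 (d = 0 to 2) or 4 (d = 3 to 20);
- at 101 days: 4 (d = 0 to 3) or 5 (d = 4 to 20).

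So 3 to 5 further infusions could precede that contact.

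**An invented example.** Day 1 is the first infusion. The last trametinib dose is on day 30, and further infusions follow on days 43, 64 and 85.

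- Visit due by 30 + 28 = day 58, which is 85 − 58 = 27 days before the last infusion.
- Reporting window under 8.1 closes on 85 + 30 = day 115, which is 115 − 58 = 57 days after the visit deadline.
- Each further infusion adds 21 days to both gaps.

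**What is not repeated later?** The schedule places immunogenicity samples in cycles 1 and 2 and at End of Treatment only. If the End of Treatment sample is drawn by day 58 in the example, no sample follows the last infusion.

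**The case against.** The strongest reply has four parts.

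First, the definition in 6.5 is attached to the biopsy sentence, and 4.5.2 triggers the visit when a subject is discontinued from treatment. A patient still being infused has not plainly been discontinued. On that reading the visit follows the last infusion and nothing is lost. This stands as a possible reading, but it does not settle the matter: 6.6 is explicit about trametinib, and no passage says which date governs when the two differ.

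Second, no passage states that CDX-3379 continues alone after a permanent trametinib stop. Section 1.6.2 speaks of holding drugs, and 5.4.2 leaves room for other criteria for discontinuation. That is correct. Single-drug continuation is implied, not stated. Equally, no passage says that CDX-3379 stops with trametinib.

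Third, a reader might infer that the early visit is the patient's last safety and disease assessment, and that PFS and duration of response are therefore disturbed. The documents do not support that. Section 6.4 keeps day-1 visits for every CDX-3379 cycle and disease evaluation every 12 weeks from the first CDX-3379 dose. Section 8.1 continues adverse event reporting, and 4.5.2 requires a scan before termination from the study. OS follow-up runs to death under 7.2, whatever the date of the first call.

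Fourth, the group is small. A reader might add the 7% ejection-fraction decreases and 10% ocular events in Section 1.4.2 and call 17% an upper limit. It is not one. The ocular events occurred mostly above 2 mg daily, not every event requires a permanent stop, and pneumonitis, which does under Table 1, is left out. The number probably is small, but it cannot be derived from the documents.

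**Conclusion.** The point holds as an inconsistency between anchors that can misplace one visit. It rests on two assumptions: that the trametinib definition in 6.5 also governs the End of Treatment visit, and that CDX-3379 may continue after trametinib stops for good. Under both, and with infusions on schedule, at least one further infusion always falls inside the 28-day window. The patient then has no scheduled post-treatment visit, laboratory draw or immunogenicity sample after the last infusion. In patients who have serial biopsies (all of phase Ib, five per arm in phase II), the progression biopsy may fall due before progression.

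The loss is limited to safety and immunogenicity follow-up in a probably small, unquantified group. Response rate, duration of response, PFS and OS are not materially affected, and the phase II design figures do not depend on it. The change is worth making because it costs almost nothing.

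**What to change.** Use one anchor date for the visit and follow-up clocks: the later of the last CDX-3379 dose and the last trametinib dose. Put it in 6.5 (for both the visit and the biopsy window) and 6.6, and refer to it in 4.5.2, 8.1 and footnotes 8, 9 and 12 of 6.7. Choose one start for survival contacts, since 4.5.2 counts from the End of Treatment visit and 6.6 from the last treatment. Naming the date in 8.1 also keeps the trametinib definition in 6.6 from being carried over to the 30-day reporting window.

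Separately, the sponsor should state whether CDX-3379 may continue alone, and reconcile 1.6.2, 5.4.2 and the treatment text in 6.2 accordingly. No dosing or stopping rule is proposed here.

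The cost is a sentence in each section and edits to three footnotes. When both drugs stop together, or trametinib stops last, the anchor date does not change. No visit or procedure is added.
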